## **2a. Situating the Researcher**

[name] is a doctorally-prepared Family Nurse Practitioner certified by the American Nurses Credentialing Center and licensed to practice in the state of Texas. A member of the Southern Nursing Research Association, [name] has experience designing and conducting qualitative and quantitative research and mixed-methods studies. Her doctoral dissertation was a qualitative study involving a marginalized population of drug-addicted women ([name], 2013). She has also done pilot work on a population of incarcerated women using quantitative methods. [name] has a current manuscript pending review on using the interpretive phenomenological inquiry method for qualitative research. [name] is well-experienced in the protection of human research subjects. She is an expert in the promoting rigor in qualitative research design and situating its importance in medical research.

[name] is a nationally certified and practicing Family Nurse Practitioner. In addition to her research role, [name] will be the primary clinician at the research site, providing physical assessments, reviewing patient medical records and formulating the patient plan of care. Because each patient of the Lung Institute is treated using the same protocols (there are no control groups), this minimizes the conflict of interest, randomization and blinding that must occur with experimental studies.

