## **5. HYPOTHESES**

### **5a. Primary Hypothesis/Quantitative Arm**

Null hypothesis: Following autologous stem cell treatment for chronic lung disease, patients will have no improvement in pulmonary function (measured by FEV1) at six months

Alternative hypothesis: Following autologous stem cell treatment for chronic lung disease, patients will have an increase in pulmonary function (measured by FEV1) of 5 to 10% or more

Rev\_2/5/16 Page 2 of 10

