## 6. STUDY DESIGN

This study uses a concurrent mixed-methods approach to collect and analyze both qualitative and quantitative data. The *quantitative* arm will use a non-experimental, descriptive approach to measure and analyze pre- and post-stem cell treatment pulmonary function test results of treated patients. Measurement of the occurrence of adverse events will also be part of the quantitative arm.

Pre-treatment pulmonary function test results (measured by FEV1) will be compared with a six-month post-treatment pulmonary function test result (FEV1) for each patient. The aim of this method is to generalize an improvement in pulmonary function (measured by FEV1) among the general population of all individuals treated by autologous cell therapy for chronic lung disease.

The *qualitative* arm of the study uses an interpretive phenomenological approach to collect and analyze pre- and post- cell therapy anecdotal data regarding perceived quality of life among treated patients. Phenomenological research involves investigating the lived experience.

Qualitative research has several assumptions (D. Nicholls, 2009; Ritchie & Lewis, 2003). Primarily, there is no predetermined theoretical framework- rather the theory, if any, is derived from the data. Secondly, qualitative research is context-driven. Finally, qualitative researchers focus on the *emic* perspective that concerns itself with the view, perspectives and descriptions of others.

This study uses an *interpretive phenomenological analysis* (IPA) approach throughout the study from planning to data collection to analysis. This methodology is used to illuminate each participant's variation of the same general phenomenon (in this case, COPD) (Reissman, 2008; Ritchie & Lewis, 2003).

Data from both arms of the study will be combined following data collection for analysis, discussion and presentation. Safety data on adverse outcomes will be tracked and reported separately as a descriptive, quantitative analysis.

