**Research Protocol**  
**Lung Institute Dallas**

## 11. STUDY PROCEDURES

Informed Consent Form is obtained. Consent form must be complete, signed, and dated without forgeries or alterations. Information should be delivered in a manner in which the Patient and/or the patient's legal representative could reasonably be expected to understand.

A review of the patient's medical record will be conducted to approve for treatment. Approved treatment plans will be documented in the patient's electronic medical record. Medical records obtained from external providers will be kept in the patient's medical record and must include recent laboratory data, results of any outside office notes, chest x-ray results and any relevant information as required per treatment inclusions and exclusions protocol.

Prior to Bone Marrow aspiration, Adipose extraction, and Venous stem cell administration, the clinician will perform a physical assessment. Attached are the following Standard Operating Procedures (SOPs) for each type of cell therapy that Lung Institute provides to qualified candidates:

- Venous Procedure
- Adipose Extraction Procedure
- Bone Marrow Aspirate Procedure

Patient follow-up may be conducted at the Lung Institute facility or may be completed by telephone at 2 weeks, 3 months and 6 months post-treatment to measure adverse events and quality of life. Patient participation in these phone calls is voluntary. Data collected at these time points will be entered into password-protected database for data management and reporting. Patients will be issued a journal during their treatment to record quality of life indicators from the time they are discharged from the clinic until they are called for follow-up. This allows the patients to better recall how they felt/are feeling to better communicate progress during follow-up appointments/calls.

Patients will have pulmonary function testing 6 months post-treatment. This will be done at the Lung Institute facility, or by their primary care physician, or pulmonologist.

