### **12b. Statistical methods**

For the quantitative, descriptive arm of this study, sample characteristics will be collected to include age, sex and diagnosis. Pre- and post-treatment FEV1 measurements will be collected on each patient and evaluated by simple measures of central tendency (mean, median and mode). Sufficient descriptive data will be collected and reported to encourage replication of our study.

For the qualitative, anecdotal arm of the study, Lung Institute utilizes CCQ, the Clinical COPD Questionnaire to document patient's perceptions on improved quality of life. The information will be collected and interpreted by evaluating for common themes within the anecdotes. As a note regarding the rigor of qualitative research: is important in qualitative research to ensure that the study is credible and trustworthy (Smith, Flowers and Larkin, 2009). A number of guidelines for assessing this quality look toward establishing credibility. Psychologist Lucy Yardley's work in 2000 provides the principles for assessing the quality of qualitative research and how the interpretive phenomenological method can address them. First, the study must provide good *sensitivity to context*. In this study, the immersion in the clinic through field experience, the existing literature on COPD and stem cell treatment, and the anecdotes obtained

Rev\_2/5/16 Page 7 of 10

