## **H. FOLLOW-UPS**

1. LI CONDUCTS A FOLLOW-UP EVALUATION VIA A TELEPHONE CALL AT 2 WEEKS.
  - a) TWO CALL ATTEMPTS ARE MADE.
2. LI CONDUCTS AN ADDITIONAL FOLLOW UP PHONE CALL CONDUCTED AT 12 WEEKS.
  - a) TWO CALL ATTEMPTS ARE MADE.
3. PATIENT IS ADVISED TO RETURN TO CLINIC AT 6 MONTHS FOR EVALUATION, LABS, PULMONARY FUNCTION, PULSE OXIMETRY AND SIX MINUTE WALK TEST.
  - a) IF RETURN TO CLINIC IS NOT POSSIBLE DUE TO DISTANCE, THE PATIENT IS ADVISED TO GO TO A LOCAL PHYSICIAN FOR EXAMINATION, LABS, PULMONARY FUNCTION, PULSE OXIMETRY, AND SIX-MINUTE WALK TEST AT 6 MONTHS.
  - b) TWO CALL ATTEMPTS ARE MADE TO OBTAIN PATIENT PROGRESS VIA A QUALITY OF LIFE SURVEY.

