
10.
	
Clinic Staff conducts introductions, reviews process, and checks for Patient readiness.
 
 
• Has Clinic Staff introduced themselves? 
 
✓ Name and Roles
 
 
 
• Has Clinic Staff reviewed the procedure process for the day? 
 
✓ Go over what the Patient can expect during the days procedure
 
 
 
• Has Clinic Staff ensured Patient readiness? 
 
✓ Answer any questions the Patient may have; and
 
✓ Check to see if Patient needs to use the restroom prior to procedure.
 
 
 
 
➤ If NO > Step must be completed prior to proceeding.
 
➤ If YES > Proceed to Step 11 of this SOP

11.
	
Clinic Staff obtains vitals.
 
 
• Has Clinic Staff obtained the following vitals? 
 
✓ Blood Pressure;
 
✓ Pulse;
 
✓ Heart Rate;
 
✓ Respiratory Levels;
 
✓ SaO Levels;
 
✓ EKG (If required, per Practitioner's judgement); and
 
✓ PFT (May be obtained within the 3 days of scheduled treatment)
 
 
 
 
➤ If NO > Obtaining Patient vitals is required prior to proceeding.
 
➤ If YES > Proceed to Step 12 of this SOP

12.
	
Clinic Staff completed the subjective/chief complaint.
 
 
• Has Clinic Staff completed the Subjective/Chief Complaint? 
 
✓ Patient Complaint/Primary Reason for Visit (i.e.: Patient here for shortness of breath, second day of procedure, COPD Treatment, etc.)
 
 
 
 
➤ If NO > Step must be completed prior to proceeding.
 
➤ If YES > Proceed to Step 13 of this SOP

10Mar2016 - version 2.0

LI-001

13.
	
Is today the first treatment day for the Patient?
 
➤ If NO > Proceed to Step 16 of this SOP
 
➤ If YES > Proceed to Step 14 of this SOP

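### The six-month FEV1 may be measured at a different site from the pre-treatment test, and the plan has no way to separate a testing shift from treatment change

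*Combined protocol and SAP*

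**What the plan says.** The quantitative hypothesis in Section 5a is that "patients will have an increase in pulmonary function (measured by FEV1) of 5 to 10% or more". Section 6 sets the comparison: "Pre-treatment pulmonary function test results (measured by FEV1) will be compared with a six-month post-treatment pulmonary function test result (FEV1) for each patient". Section 2a confirms that "there are no control groups".

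For the six-month test, Section 11 allows three routes: "This will be done at the Lung Institute facility, or by their primary care physician, or pulmonologist". Policy CL-005, section H, asks the patient to come back to the clinic and gives an alternative: "IF RETURN TO CLINIC IS NOT POSSIBLE DUE TO DISTANCE, THE PATIENT IS ADVISED TO GO TO A LOCAL PHYSICIAN FOR EXAMINATION". That alternative visit includes pulmonary function. Off-site testing is thus a planned route and not a deviation.

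For the pre-treatment test, the Venous SOP (step 11) and the Bone Marrow SOP (step 9) list it among the items that clinic staff obtain before treatment: "PFT (May be obtained within the 3 days of scheduled treatment". Neither names a location. The Discharge SOP (steps 7 and 15) repeats the line, so the documents do not fix which test is the baseline if more than one is taken.

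Section 11c names FEV1 as the measurement tool and gives no device, calibration, quality standard or bronchodilator state. Section 12b says the measurements are "evaluated by simple measures of central tendency (mean, median and mode". It does not mention test location.

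**The concern.** A within-patient change in FEV1 is a difference between two readings. If the two come from different spirometers, or one before and one after a bronchodilator, the difference contains a testing component as well as any real change. With a concurrent control group measured the same way, that component could largely cancel. Here there is none, so it passes straight into the mean change. A larger sample narrows the interval but does not remove a systematic shift.

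Bronchodilator state deserves attention on the protocol's own terms. Section 13 lists less need for bronchodilator inhalers as a potential benefit, so inhaler use may differ between the two tests. This gap is distinct from test site, because it can also arise between two tests at the clinic.

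At stake is whether a reported mean gain near the 5% lower target can be read as a change in lung function. If site, device and bronchodilator state are not recorded at the time, they may not be recoverable later.

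**Working it through.** **The plan's own figure.** The only design figure is the anticipated sample of 200 (Section 12a). The documents give no SD, significance level, power or dropout rate, so it cannot be re-derived. It is used below as the number of complete pairs, which is a best case.

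**Inputs**
- n = 200 (Section 12a).
- Lower target: 5% (Section 5a). The section does not say whether this is relative change or points of percent predicted; relative change is assumed here.
- f, the share tested off-site at six months: not in the documents; assumed 0.25 to 0.75.
- b, the mean difference between outside and clinic readings as % of FEV1: not in the documents; assumed -5 to +5.
- SD of percentage change: not in the documents; assumed 10 to 20.

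**Bias in mean change = f × b**
- 0.25 × 2 = 0.5 points
- 0.50 × 3 = 1.5 points
- 0.50 × 5 = 2.5 points, half the lower target
- 0.75 × 5 = 3.75 points, which is 75% of the lower target
- 0.75 × (-5) = -3.75 points
- b = 0 gives 0

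The range is -3.75 to +3.75 points. For a bronchodilator mismatch the same formula applies, with f as the share of mismatched pairs.

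**Sampling error for comparison: 95% half-width = t × SD/√n**
- n = 200: 1.972 × 10/14.14 = 1.4; with SD 20, 2.8 points

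A bias of 1.5 points already exceeds the smaller half-width, and 3.75 exceeds the larger.

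**Illustration.** The plan specifies no test. If one were applied at two-sided 5%, with no true change, n = 200, SD 15 and f = 0.5, the chance of a nominally significant improvement is 1 - Φ(1.96 - f × b/SE). The SE is √(15² + f(1-f)b²)/√200.
- b = +2: 15%
- b = +3: 29%
- b = +5: 64%

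The nominal figure in that direction is 2.5%. Negative shifts of the same size give the same chances of a spurious decline.

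**If office differences are purely random.** With mean difference zero, the mean change is unbiased and only noise rises. With no true change, within-patient SD 10 and device SD 5, the share of off-site patients showing a gain of at least 5% moves from 1 - Φ(5/10) = 30.9% to 1 - Φ(5/√125) = 32.7%.

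**Precision of a same-site subset**, assuming clinic baselines:
- f = 0.50 leaves 100 pairs: 1.984 × 10/10 = 2.0; with SD 20, 4.0 points
- f = 0.75 leaves 50 pairs: 2.010 × 10/7.07 = 2.8; with SD 20, 5.7 points

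A requirement to match bronchodilator state as well would reduce these numbers further.

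**The case against.** The strongest reply is that nothing shows a bias exists. Outside tests would come from many separate offices, and if their differences from the clinic centre on zero, the mean is unaffected and the extra noise is small. That stands as a possibility, and it is why the range includes zero and both signs. It is not an assurance: the clinic's own equipment would be common to every off-site pair with a clinic baseline, so an offset there would not average out over outside offices.

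A second reply is that the FEV1 arm is described as descriptive. It is uncontrolled, and CL-005 section G also recommends rehabilitation, supplements and nebulizer treatment afterwards. Consistent testing would not make the change attributable to the cell treatment. That also stands. The gain is narrower: the trial could see whether a testing shift drives its result.

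A reader might go further than the documents allow in four ways.
- That baseline is definitely measured at the clinic. This is inferred from the SOPs; Section 11 does not say so. If some baselines were also external, the comparability problem would remain.
- That site differences inflate the result. Neither sign nor size is known.
- That sicker patients are tested elsewhere. CL-005 gives only distance as the reason.
- That same-site pairs should therefore be the primary analysis. Returning to the clinic is a choice made after treatment, so that restriction could exchange an unknown measurement bias for a selection bias, with fewer patients.

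**Conclusion.** The point holds as a gap in measurement and reporting, not as a demonstrated bias. The documents plan for off-site six-month tests, set no common measurement conditions, and provide nothing in Section 12b that distinguishes those pairs. A systematic difference between sites or bronchodilator states would therefore be indistinguishable from treatment change. Under the assumed off-site share and shift, it could move the mean change by up to 3.75 points either way, or not at all. At the larger assumed values this exceeds the sampling error of the full sample and is a substantial part of the 5% lower target. These sizes rest wholly on the assumed f, b and SD. The defect itself rests on the text, apart from the inference about where baseline is measured.

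**What to change.** **Data collection (Sections 11 and 11c, CL-005 section H).** For every FEV1, record the test site, the device and whether the reading was before or after a bronchodilator. Ask all testers, including outside ones, to use the same bronchodilator state as the baseline test. Patients may still be tested locally.

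**Analysis (Section 12b).** Keep all pairs as the main analysis. Pre-specify a sensitivity analysis in pairs with the same site and bronchodilator state. Report the change separately for clinic-tested and outside-tested patients. State with these results that patients who return are self-selected, by distance according to CL-005, so a difference between the groups need not be a measurement effect.

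**Cost.** Three data fields, a request to outside testers and one extra table. The sample size does not change. The sensitivity estimate will be less precise, as shown for 100 and 50 pairs; at 50 pairs and SD 20 its half-width exceeds the 5% lower target, so it may be inconclusive.

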#### **11a. Recruitment of participants**

Patients are included in treatment by self-referral. Patient coordinators conduct a series of questions with prospective patients to determine initial candidacy. If prospective patients are found to meet candidacy criteria, records are obtained to be reviewed by the mid-level provider and/or physician to determine final eligibility and approval for treatment.

#### **11b. Randomization**

Neither the participants, nor the investigator, or those assessing/analyzing the outcome(s), will be blind (or masked) to group assignment; all patients will receive treatment.

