## **3. AIM(S) OF STUDY**

Through the collection of qualitative and quantitative data, Lung Institute aims to explore and describe the safety and efficacy of autologous stem cell treatment for chronic lung disease with dissemination to the public and to the medical community for the advancement of regenerative medicine. The study aims to confirm the safety of autologous cell therapy, explore the effect of autologous cell therapy treatment on pulmonary function, and to describe the anecdotal quality of life changes of patients following treatment using both quantitative and qualitative measures.

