## **4. RESEARCH QUESTIONS**

The research questions to be informed by this investigation are as follows:

1. Is the collection and administration of autologous stem cells for the treatment of chronic lung disease safe?
2. Does treatment with autologous stem cells for chronic lung disease improve measurements of pulmonary function (specifically FEV1)?
3. Does treatment with autologous stem cells for chronic lung disease improve the patient's perceived quality of life?

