## **Research Protocol Lung Institute Dallas**

from the participants will contribute to building an awareness of the phenomena. Awareness of the patient, empathy, active listening, and providing comfort to the participants will be used (Smith et al., 2009).

Yardley's second broad principle is *commitment*. Commitment comes from the degree of attentiveness to the participant during the interview, the thoughtfulness of the work, and the completeness of the analysis undertaken. As described, the analysis needs to be conducted systematically and also be sufficiently interpretative- rather than simply describing, the analysis must also be interpretive and reflective. The third broad principle is *transparency* and how clearly the stages of the study are presented to the reader. This principle suggests a careful description of how the participants were selected, how the interview was conducted and the steps used to analyze the data. Also the study must provide cohesiveness, and the themes need to mesh together logically. With this, the foundational steps of the IPA method need to be clearly demonstrated (Smith et al., 2009). In this study, each stage of the study will be defined in the presentation of data. This will allow another researcher to replicate the study if desired.

Yardley's fourth principle, *impact and importance*, relates to the study's ability to tell the researcher something interesting, important or useful" (Smith et al., 2009). This study will inform the public and medical community on the safety and efficacy of autologous stem cell treatment for chronic lung disease.

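### The single-group before-and-after comparison of FEV1 cannot show that treatment improves lung function or quality of life, so the efficacy wording should be cut back to describing change

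*Combined protocol and SAP*

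**What the plan says.** **Design.** Section 2a states that "there are no control groups". Section 11b adds that nobody is masked and that "all patients will receive treatment". Section 6 sets out a "non-experimental, descriptive approach to measure and analyze pre- and post-stem cell treatment pulmonary function test results", comparing one pre-treatment FEV1 with one six-month FEV1 in each patient. Section 12b plans only the mean, median and mode.

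**Claims.** The second research question in Section 4 opens "Does treatment with autologous stem cells for chronic lung disease improve measurements of pulmonary function (specifically FEV1"; the third asks whether treatment will "improve the patient's perceived quality of life". Section 3 sets out to "explore and describe the safety and efficacy of autologous stem cell treatment for chronic lung disease". Section 6 says: "The aim of this method is to generalize an improvement in pulmonary function", meaning among all individuals given this therapy for chronic lung disease. Section 12b ends: "This study will inform the public and medical community on the safety and efficacy of autologous stem cell treatment for chronic lung disease". Section 5a takes an FEV1 rise of 5 to 10% or more as its alternative hypothesis. The same rise is a hypothesised outcome in Section 1 and a potential benefit in Section 13.

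**Stated limits.** Section 14 accepts that results may not carry over to people who cannot pay. No section says that a change cannot be attributed to treatment. Section 2a presents the lack of a control group as an advantage.

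**The concern.** Whether treatment improves FEV1 is a causal question. It asks how FEV1 at six months compares with what it would have been in the same patients without the cells. A single treated group observed before and after has no estimate of that second quantity. The documents supply no untreated course and no historical rate, and they do not plan to use spirometry from before the pre-treatment test.

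What is at stake is the study's main conclusion. The results are meant for the public as well as the medical community, and Section 14 says the treatment is provided for a fee. A correctly calculated mean change could be read as evidence of efficacy that the design cannot provide. The same holds for quality of life, which is self-reported by patients who know they were treated.

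**Working it through.** **1. Claim against design.** To answer the Section 4 questions, the plan would need an estimate of six-month FEV1, and of the questionnaire score, without treatment. Sections 2a, 6, 11b and 12b provide none. This step needs no assumed figure.

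**2. What the mean change contains.** If the cells had no effect, the expected change in mean FEV1 would be

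regression to the mean − natural decline + co-interventions + test-site differences + selective return.

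The documents give grounds for every term and a size for none:

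- Regression to the mean: entry is by self-referral (Section 11a). Any low-point entry would make the pre-treatment value atypical.
- Natural decline: Section 1 describes it for COPD but gives no rate. It lowers the change.
- Co-interventions: inhaled glutathione (Venous SOP step 22, Discharge SOP step 12); nebulizer solutions, supplements and recommended pulmonary rehabilitation (CL-005 part G).
- Test site: six-month spirometry may be done by an outside physician (Section 11, CL-005 part H).
- Selective return: patients are only advised to come back at six months (CL-005 part H).

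With terms of opposite sign and unknown size, the net direction of bias is unknown.

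**3. Hypothetical size of one term.** Let σ be the within-patient SD as a percentage of FEV1, and k the number of SDs below the usual level at entry. Apparent gain with no effect = k × σ. Both inputs are assumed (σ from 5 to 10%, k from 0 to 0.5). The Section 5a target is read as a relative change, which the protocol does not specify.

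| k | σ = 5% | σ = 10% |
|---|---|---|
| 0 | 0% | 0% |
| 0.25 | 1.25% | 2.5% |
| 0.5 | 2.5% | 5% |

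Only the bottom right cell reaches the 5% target.

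**4. Sample size does not help.** The anticipated 200 patients (Section 12a) come with no test, error rate, power or SD, so the figure cannot be reproduced or called wrong. With an assumed SD of change of 10 to 20 points, the 95% half-width is 1.96 × SD / √200 = 1.4 to 2.8 points. A larger sample narrows that interval but leaves the terms in step 2 unchanged.

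**5. What earlier spirometry could add.** Suppose there is no treatment effect and no trend. The earlier value is U, the first-day value is U − b (low by b), and the six-month value is U.

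- Change before treatment: −b. Change after: +b. Their contrast is 2b, which looks like a reversed decline.
- Six-month value against the average of the earlier and first-day values: b/2.
- Six-month value against the earlier value: 0.

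Contrasting the two changes counts the low value twice. It is also noisier: with independent errors of equal size its variance is (1 + 4 + 1)σ² = 6σ², against 2σ² for the simple change, so the SD is √3 = 1.73 times larger. The direct comparison avoids the double counting, but includes any real decline over the longer interval.

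**The case against.** The wording is not uniformly causal. Section 3 says explore and describe, and Section 6 says descriptive. The efficacy sentence in Section 12b illustrates a principle of qualitative rigour; it is not a decision rule for FEV1. Section 14 rules out promising patients a definite improvement, and part C of CL-005 requires that no guarantees be made. These points are fair and soften the tone, but they do not withdraw the research questions in Section 4 or the generalising aim in Section 6.

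A reader might infer that any positive mean change will be sold to patients as efficacy. The documents do not say so, and Section 5a sets a target of 5 to 10% or more.

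A reader might also infer that patients enroll when they are at their worst, so that regression to the mean explains the hoped-for gain. Section 11a says only that they refer themselves. The exclusions in Section 9b for active infection and for recent hospitalisation with ventilation may limit low-point entry, and the stated decline works against an apparent gain. An offset of zero is possible, so the figures above show only what could happen.

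Finally, earlier spirometry is not a named required record in Section 11 or in step 2 of the Venous SOP. It may have to be requested, and it will be incomplete. That objection stands, and it is why the check is optional.

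**Conclusion.** The point holds as a conflict between design and conclusion. A single-group, unmasked, descriptive comparison of two FEV1 values is asked to show that treatment improves FEV1 and quality of life, to generalise that improvement, and to inform the public about efficacy. It cannot attribute a change to the cells. That rests on the text alone and should be corrected.

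The size and direction of the bias are not known. The 0 to +5% from regression to the mean depends on an assumed within-patient SD of 5 to 10% and an assumed entry offset of 0 to 0.5 SD, and it covers one term only. The documents do not support saying that the result will be biased upward, that 200 patients is the wrong number, or that a descriptive study without a control arm is invalid. It is valid for describing change.

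**What to change.** **Wording.** Reword Sections 1, 3, 4, 5a, 6, 12b and 13 consistently, so that the stated purpose is to describe the change in FEV1 and in the Clinical COPD Questionnaire six months after treatment. State in the protocol and in every report that, without a comparison group, no efficacy conclusion will be drawn and changes will not be attributed to treatment. Changing only some of these sections would create a new contradiction, for example with the alternative hypothesis in Section 5a. Sections 5c and 10 also anticipate improvement and should be read for consistency.

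**Optional partial check.** Where records contain earlier spirometry, abstract it. Report how many patients have it and whether they differ from the rest. Compare the six-month FEV1 directly with the earlier values as well as with the first-day value. Do not rest the check on the change before against the change after treatment. State that the check cannot address co-interventions, test site, loss to follow-up or the questionnaire.

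**Cost.** The rewording costs text and a less favourable claim. The check costs modest abstraction work, possibly some record requests, and yields incomplete data. No control arm is asked for.
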